CID	Boston Medical Center Infectious Disease Clinic (HIV clinic)
ARCH	Active Retention in Care in Health
CBO	Community-Based Organization
EHR	Electronic Health Record
MRN	Medical Record Number
ITT	Intention to Treat
BUMC	Boston University Medical Campus

Protocol Summary

Title:	CAB-RPV LA Implementation Strategies for High-Risk Populations
Population:	
 • HIV-infected persons age \geq 18 years, English or Spanish speaking • Virally suppressed at time of enrollment (Cohort 1 or Cohort 2 - CAB-RPV LA cohorts)
Intervention:	CAB-RPV LA in CBOs
Objectives:	Pilot-test strategies for implementing CAB-RPV LA in non-HIV clinic settings
Design/Methodology:	
Design: Three-arm cohort study comparing CAB-RPV LA delivered outside of standard clinical settings to CAB-RPV LA delivered in the HIV clinic setting and to standard care (HIV treatment delivered in the HIV clinic) utilizing EHR data
 
Methodology: mixed methods (qualitative, quantitative)

Total Study Duration:	
24 months for total study (Objectives 1-3)
 
12 months for Objective 2 only (current protocol); It is anticipated that final data analysis could take up to an additional 12 months.

Subject Participation Duration:	Six months.

Protocol Title: **CAB-RPV LA Implementation Strategies for High-Risk Populations**

1.0 Background & Rationale

1.1 Background

Studies have shown that People Living with HIV (PLWH) who stay in care, adhere consistently to ART, and achieve viral suppression have little to no risk of HIV transmission (Cohen et al., 2016); this means that ensuring retention and treatment adherence among PLWH is critical for HIV prevention. However, social determinants of health, such as poverty, homelessness, substance use, mental health disorders, and a history of incarceration, can elevate the risk of non-adherence and retention in traditional, clinic-based HIV care for some populations. The added complication of the COVID-19 pandemic and the resulting challenges around accessing medical care within traditional settings have made adherence increasingly difficult for PLWH. Alternative models to support ART adherence and retention in care are the foundation of achieving viral suppression and curbing HIV transmission for these vulnerable and high-risk populations.

Cabotegravir-Rilpivirine Long Acting (CAB-RPV LA) has been proven clinically effective and is fully approved by the FDA. In addition to its efficacy, CAB-RPV LA has shown promising potential as an alternative treatment modality to improve adherence for populations at the highest risk for falling out of care. CAB-RPV LA can be administered as a monthly or bi-monthly injection and thus may address multiple adherence-related challenges faced by high-risk populations, including the need to remember a daily pill, the lack of a place to refrigerate medications, and side effects, as the medication has been found to be well-tolerated (Swindells et al., 2019). Qualitative data collected in the first objective of this project have shown that a majority of patients interviewed would prefer the injection in comparison to their usual daily oral medication, and believe that an injection would increase their ability to adhere to treatment. They would also strongly prefer that injection to be delivered in a setting that they frequent, often outside of the HIV clinic.

At the same time, CAB-RPV LA requires a monthly or bi-monthly injection in order to be effective, thereby necessitating more frequent interaction with a provider than with oral HIV medication. Injection administration typically takes place in an HIV clinic or similar healthcare setting. This higher level of touch may present challenges for patients, including transportation costs, lost wages for visits during clinics' typical hours that coincide with the workday, and stigma. Patients also need to be engaged with their healthcare provider. Overcoming these barriers by facilitating and promoting CAB-RPV LA's acceptance and implementation in community-based settings and among patients, providers, and organizations will significantly contribute to ending the HIV epidemic.

This study will be conducted in compliance with the protocol, applicable regulatory requirements, and Boston Medical Center/Boston University (BMC/BU) Medical Campus Human Research Protection policies and procedures.

1.2 Rationale & Purpose

Our proposed implementation research is designed to evaluate a novel approach to engage individuals with HIV who are at the highest risk for not accessing care or adhering to treatment. We are not testing CAB-RPV LA; this is an approved drug. We are also not studying the drug nor are we studying it for a new population, new dosage or new route of administration. Rather, we are conducting an implementation study and propose to test implementation CAB-RPV LA in community-based settings.

Strategies to implement evidence-based interventions to end the HIV epidemic are urgently needed. Despite highly effective antiretroviral treatment (ART) for HIV infection and multiple effective prevention interventions, there are approximately 40,000 new HIV infections annually in the US (CDC, 2019). Two of the four pillars of the US Department of Health and Human Services "Ending the HIV Epidemic" initiative are to:

Protocol Title: **CAB-RPV LA Implementation Strategies for High-Risk Populations**

1) treat individuals with HIV rapidly and effectively to achieve viral suppression; and 2) prevent new infections by using evidence-based interventions (<https://www.cdc.gov/endHIV/>).

Our implementation research addresses three ViiV Healthcare priority areas: 1) implementation of CAB-RPV LA delivery models in non-HIV clinic settings; 2) feasibility and acceptability of bringing CAB-RPV LA injections to the patient (rather than bringing the patient to the medication in more traditional ways only); and 3) addressing challenges of CAB-RPV LA delivery amongst high risk populations, specifically women and men of color, immigrants, homeless individuals, active substance users, transactional sex workers, individuals released from incarceration, and individuals who have fallen out of HIV care. Our study (which overall incorporates three Objectives) addresses the following research questions:

A. Implementation Questions

1. Will community-based delivery of CAB-RPV LA be an acceptable and feasible delivery method to high-risk PLWH from the patient, provider and community organization perspectives? (acceptability/feasibility)
2. Can a community-based delivery strategy lead to initiation and completion of injections for six months for at least 80% of individuals who are enrolled into Cohort 1 for an initial visit in an outreach setting? (reach)
See Section 11 for information on the details of the sample size calculations and Section 7.2 for how study staff will stay in contact with participants to maximize potential for longer term engagement.
3. What are the characteristics of patients who are most likely to have an initial injection and do these characteristics differ for individuals who receive CAB-RPV LA in and outside of the HIV clinic? (equity)
4. Are patients who are seen for CAB-RPV LA in community-based settings satisfied with their HIV care? (patient-centeredness)
5. Will consistent delivery of CAB-RPV LA be possible in community-based (non-HIV clinic) settings? (feasibility)
6. Will the providers at a drop-in center or community-based organization be willing to implement CAB-RPV LA within their non-traditional setting? (adoption)

B. Clinical Questions

1. Can individuals targeted for intervention at community-based delivery site achieve viral suppression and receive initial injection?
2. Can a community-based delivery strategy ensure engagement in services and receipt of CAB-RPV LA visits among high-risk populations? (effectiveness)
3. Is a community-based delivery strategy using CAB-RPV LA superior to the current standard of care in ensuring treatment adherence for individuals at highest risk? (effectiveness) Can high-risk individuals who receive community-based CAB-RPV LA be adherent to care, defined as undetectable viral load, for six months?

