5.2 Subject Exclusion Criteria

Individuals who are not HIV positive, individuals under the age of 18 and individuals who do not speak English or Spanish will be excluded. Individuals who are not virally suppressed prior to beginning CAB will be excluded (excluding Cohort 3). Individuals who are not willing to take CAB-RPV LA after detailed discussion of what the use of CAB-RPV LA will entail, or are unable to undergo clinical eligibility testing to confirm eligibility will be excluded (excluding Cohort 3). If they have a history of integrase inhibitor mutations suggesting resistance to Cabotegravir or Cabenuva, a history or evidence of resistance to either INSTI or NNRTI, are currently pregnant or breastfeeding, or have HIV 1 with an HIV 2 co-infection or an HIV 2 infection, they will also be excluded. Individuals who have hepatic impairment at baseline lab draws will be excluded. Individuals who are on drugs that have known interactions with Cabenuva (including but not limited to carbamazepine, oxcarbazepine, phenobarbital, phenytoin, St Johns Wort, systemic Dexamethasone, rifabutin, rifampin and rifapentine) will be excluded. Individuals who have chronic Hepatitis B infection will also be excluded. If an individual is receiving CAB-RPV LA at CID, they are not eligible for Cohort 3.

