- If a potential participant is a BMC patient, study staff will obtain consent to move forward with the participant's care team in order to determine that the potential participant is eligible for the study.

All decisions will be made by study clinicians who will review medical documentation to determine that the potential participant meets eligibility criteria. Participants must be virally suppressed prior to enrollment, meaning that their HIV-1 ribonucleic acid measures less than 50 copies per mL. If a potential participant's EHR review indicates that they have a history of integrase inhibitor RT mutations suggesting resistance to Cabotegravir or Cabenuva, have demonstrated they have resistance to either an INSTI or an NNRTI, that the potential participant is currently pregnant, breastfeeding, or that the potential participant has HIV 1 with an HIV 2 co-infection or an HIV 2 infection, they will be deemed to be ineligible. Individuals who are not HIV positive, individuals under the age of 18 and individuals who do not speak English or Spanish are also ineligible. Individuals who are not virally suppressed are ineligible. Individuals who are not willing

Protocol Title: **CAB-RPV LA Implementation Strategies for High-Risk Populations**

to take CAB-RPV LA after detailed discussion of what the use of CAB-RPV LA will entail, or are unable to undergo clinical testing to confirm eligibility will be excluded. Individuals who are on drugs that have known interactions with Cabenuva, including but not limited to carbamazepine, oxcarbazepine, phenobarbital, phenytoin, St Johns Wort, systemic Dexamethasone, rifabutin, rifampin and rifapentine. Individuals who have chronic Hepatitis B infection will also be excluded. All women with child-bearing potential will have a pregnancy test conducted at a CLIA approved lab to rule out pregnancy.

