Study staff will contact every individual who was screened within two weeks of screening (once test results are received and study clinician has confirmed whether or not they are eligible) and let them know if they are eligible for enrollment. Study staff will ask eligible individuals to return to PT for final study enrollment. If the potential participant is ineligible for enrollment due to being unsuppressed, study staff will encourage the potential participant to re-engage in their care in order to achieve suppression, and reach out to study staff once their viral load is undetectable for enrollment. If potential participants are ineligible for enrollment based on other criteria, study staff will refer back to clinical staff from PT to make an appropriate referral.

Once an individual in Cohort 1 is determined eligible and agrees to participate, they will meet with study staff at PT to complete the consent form to enroll in the study. Study enrollment will involve the following procedures:

- Study staff will contact the participant within 2 weeks of initial screening if participant is eligible for participation to schedule a meeting date for full consent procedures, and to collect baseline questionnaire data, as described above. Study staff will log this contact in the study log book (Appendix H).
- Prior to the consent and initial survey meeting, study staff will create a folder that contains a copy of the participant's screening consent form (Appendix A), a blank enrollment consent form (Appendix B), a blank Electronic Health Record Review Form (Appendix E), a blank Participant Questionnaire (Appendix F), and a blank Locator form (Appendix G). This folder will be labeled with their individual Study ID. The study ID key will be the following: Study ID Key: O2XXX – XXX is the equivalent of the number patient that they are. For example, the first person to be consented and enrolled into the study will be Participant Number O2001. The project manager will assign this number when participants are enrolled. This key will be used for participants in all three cohorts.

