11.0 Statistical Plan

11.1 Study Hypotheses

Objective 2 has the following hypotheses:

- **H1:** Changing the service site will result in $\geq 80\%$ of participants in the community-based intervention arm beginning injections
- **H2:** Of participants in the community-based intervention arm who begin injections, 80% will complete 6 injections
- **H3:** Changing the service site will result in improved engagement in care for participants in the community-based intervention arm compared to matched controls (Cohort 3) at 6 months for intervention patients compared to control group patients
- **H4:** Changing the service site will result in superior HIV viral suppression at 6 months compared to for participants in the community-based intervention arm compared to matched controls (Cohort 3)
- **H5:** Participants in the community-based intervention arm will be equally satisfied with their care compared to patients who receive care in clinic settings (Cohort 2).

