11.2 Sample Size Calculation

For the pilot study, we have powered our study to address hypothesis 4 above. Our power calculation is as follows: With a total of 60 participants, 20 patients in each cohort, the study will have the statistical power to detect clinically meaningful differences in both engagement in care (appointment adherence) and undetectable viral load at 6 months. Depending on appointment adherence and undetectable viral load in the standard of care control group, we will be able to detect a minimum 40% difference, assuming 80% power and type 1 error probability (alpha) = 0.05. Estimates from our study sites suggest that undetectable viral load can be as low as 50% at any given time in our high-risk population. If we observe this level in the standard of care control group at 6 months, we will be able to observe a difference of 40% (or 90% vs. 50%) between the Cohort 1 CAB-RPV LA in the CBOc arm vs. the Cohort 2 CAB-RPV LA in the clinic arm and Cohort 1 CAB-RPV LA in the CBO arm vs. Cohort 3 no CAB-RPV LA arm participants, respectively. Because our intention to treat (ITT) analytic approach may mean an even lower proportion in controls (because missing data will be considered detectable), we believe our sample size is sufficient to yield rigorous clinical outcomes.

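### The viral-suppression half of clinical question B1 is settled by the entry criteria, because no planned analysis uses the people who were screened

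*Combined protocol and SAP*

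**What the plan says.** Section 2.0 commits the study to examining the questions listed in Section 1.2. Three of those, and one hypothesis, matter here.

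- **B1** (Section 1.2): "Can individuals targeted for intervention at community-based delivery site achieve viral suppression and receive initial injection".
- **A3** (Section 1.2, labelled equity): which patients are most likely to have a first injection, and whether their characteristics differ inside and outside the HIV clinic.
- **A2** (Section 1.2, labelled reach): starting and completing six months of injections in "at least 80% of individuals who are enrolled into Cohort 1 for an initial visit in an outreach setting".
- **H1** (Section 11.1): at least 80% of the community-based arm begin injections.

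Entry to Cohort 1 is filtered. Section 7.1: "Participants must be virally suppressed prior to enrollment, meaning that their HIV-1 ribonucleic acid measures less than 50 copies per mL". Section 5.2 also excludes "Individuals who are not willing to take CAB-RPV LA after detailed discussion of what the use of CAB-RPV LA will entail", along with people who have resistance, hepatic impairment, interacting drugs and other conditions. A person found unsuppressed at screening is encouraged to re-engage in care and to "reach out to study staff once their viral load is undetectable for enrollment". No time window, count or outcome is set for that person. The study ID is assigned at enrolment (Section 7.1).

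Section 5.1 defines Cohort 2 as people already receiving CAB-RPV LA at the clinic. Sections 11.1 to 11.3 contain no analysis of people who were screened and not enrolled.

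**The concern.** B1 asks about an achievement, and the analysis set holds only people who had achieved it before they entered. Within enrolled Cohort 1 the answer to that half of the question is yes for everyone, whatever the delivery model does.

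A3 has a related gap. Describing who is likely to start needs people who did not start. Cohort 2 has none by definition, and Cohort 1 has few if the study succeeds on H1.

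At stake is how a good result would be read. The population named in Section 1.2 includes people who have fallen out of HIV care, whom a suppression criterion is likely to screen out. A start rate of 80% or more among enrolled people, reported under the label of reach, could be taken as the share of that population the model can serve.

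**Working it through.** **1. The plan's own sample size.** Section 11.2 gives 20 per cohort for 90% vs 50% undetectable, 80% power, alpha 0.05. Taking a two-sided test with pooled variance and no continuity correction (the plan does not state sidedness):

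n = [1.960 × √(2 × 0.7 × 0.3) + 0.842 × √(0.5 × 0.5 + 0.9 × 0.1)]² / 0.4² = 19.4, rounded up to 20.

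The figure reproduces. It concerns H4. No sample size or precision is given for H1, B1 or A3.

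**2. B1 against the eligibility rules.** B1 has two parts.

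| Part of B1 | Who is observed under the plan | Can the answer vary? |
|---|---|---|
| Achieve suppression | Enrolled Cohort 1, all below 50 copies/mL at entry | No |
| Receive first injection | Enrolled Cohort 1 | Yes |

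Only the first part fails.

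**3. A3.** Cohort 2 contributes 0 non-starters. In Cohort 1, H1 is met with at least 0.80 × 20 = 16 starters, which leaves at most 20 − 16 = 4 non-starters.

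**4. Enrolled versus screened denominator.** Let s be the proportion suppressed at screening, and suppose suppression is the only filter. Then 20 enrolled come from 20/s screened, and 16 starters are 16/(20/s) = 0.80 × s of those screened.

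| s | Source | Screened for 20 enrolled | 16 starters as share of screened |
|---|---|---|---|
| 50% | Low figure, Section 11.2 | 40 | 40% |
| 70% | Assumption | 28.6 | 56% |
| 90% | Assumption | 22.2 | 72% |

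In each row H1 is met while the screened-based share is below 80%. Precision is low on either base: the exact 95% confidence interval is 56% to 94% for 16/20, and 25% to 57% for 16/40. People who later become suppressed and return would raise the screened-based share. Resistance, other exclusions, refusal or failure to return would lower it.

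**5. Does the filter make H1 certain?** The chance of at least 16 starters among 20, from the binomial distribution:

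| True start rate among enrolled | Chance of meeting H1 |
|---|---|
| 75% | 41% |
| 80% | 63% |
| 85% | 83% |
| 90% | 96% |
| 95% | 99.7% |

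The documents give no start rate, so they do not show which row applies.

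**The case against.** **The H1 denominator is disclosed.** A2 says enrolled and H1 says participants in the arm. This stands, and H1 is not wrong as written.

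**A reader might infer that H1 is close to automatic, because everyone enrolled is suppressed, eligible and willing.** The documents do not support this. After enrolment there are still required laboratory results, no same-day injection and an optional lead-in of up to 28 days (Section 7.1), then prior authorization and pharmacy collection (Section 7.5), all in a group chosen for poor engagement. Step 5 shows that H1 is near certain only if the true start rate is about 90% or more.

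**A reader might also infer that B1 cannot be answered at all.** That goes too far. The injection half can be answered among enrolled people. The suppression half is unanswered by the planned analysis, but screening data exist that could give it a denominator.

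**The 40% is one scenario.** The plan says "undetectable viral load can be as low as 50% at any given time in our high-risk population" and applies the figure to the control group at 6 months, not to people screened for Cohort 1. Section 7.1 pre-selects: staff at two sites approach people who appear to meet or do meet the criteria, and the flyer at the third lists them. Suppression among those screened may well exceed 50%. This stands, which is why a range is shown.

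**A screening table would still not describe the whole high-risk population, and its data are thinner.** Both points stand. The baseline questionnaire is given only at study consent (Section 7.3), and no later record review is described for people who are not enrolled.

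**A3 also asks whether characteristics differ between settings, and Section 11.3 plans a baseline comparison of Cohorts 1 and 2.** True, but that comparison describes two groups of mostly or wholly treated people. It does not show who fails to start.

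**Conclusion.** The concern holds in a limited form. Under the plan as written, the suppression half of B1 is true by selection, and the start/no-start contrast in A3 rests on at most 4 non-starters in Cohort 1 if H1 is met and none in Cohort 2. The first conclusion follows from the eligibility text and the absence of any screened-population analysis; it needs no assumed figure.

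H1 stands on its enrolled denominator. It is conditional on prior suppression, eligibility and willingness, so it measures starting among people who passed screening. The gap between that and reach among those screened could be large (80% against 40%) or modest (80% against 72%). That range assumes that suppression is the only filter, and two of its three suppression rates are assumptions.

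The change is worth making because it is cheap and gives B1 a denominator in which the answer can vary. It does not call the design or H1 into question.

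**What to change.** 1. Keep H1 and A2 on enrolled people.
2. Assign an identifier at screening consent and keep a screening log for Cohort 1.
3. Answer B1 on everyone who signed the screening consent, in one table: screened → suppressed at screening → returned and re-screened as suppressed (counted only from those who return) → eligible → enrolled → first injection. Give exact 95% confidence intervals.
4. State the denominator for each of B1, A2, A3 and H1.
5. For A3, compare injected with not-injected screened people at the community site descriptively, using only EHR variables reviewed at screening. State that Cohort 2 supplies no non-starters.
6. Before defining the suppression step, reconcile Section 7.1 with itself: it describes suppression as less than 50 copies/mL at enrolment, but writes it with the opposite inequality sign for participants who skip the lead-in.

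Most of the material exists. Viral load and genotype are reviewed after screening consent (Section 10.1), and every screened person is contacted within two weeks (Section 7.1). No eligibility or clinical rule changes.

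The costs are a small amount of log-keeping, a less favourable reach figure, and no questionnaire data on people who do not enrol. The investigator must confirm that the screening consent, described in Section 7.1 as access to records to determine eligibility, permits this use. The report should say that the table describes people approached and screened, not the whole high-risk population.
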